1.4.2.3. Clinical Safety and Preliminary Efficacy for BGB-290-AU-002

BGB-290-AU-002 is a first-in-human study evaluating BGB-290 to characterize the safety, the MTD, preliminary antitumor activity, and the PK of BGB-290 given as a monotherapy in a 3+3 dose escalation scheme. BGB-290 was administered in doses ranging from 2.5 to 120 mg PO BID.

The study is being conducted in 3 Australian study centers, and preliminary data for 45 patients are available (cutoff date of 30 September 2016).

The preliminary safety data indicate that the most frequent nonhematologic adverse events (AEs) ($\geq 10\%$ of patients) assessed as related to BGB-290 were nausea (51%, $n = 23$), fatigue (29%, $n=13$), vomiting (18%, $n = 8$), diarrhea (16%, $n = 7$), and decreased appetite (11%, $n = 5$).

Hematologic AEs are of interest in this study. The most frequent hematologic AEs ($\geq 10\%$ of patients) assessed as related to BGB-290 were anemia (22%, $n = 10$) and neutropenia (11%, $n = 5$). Hematologic AEs, regardless of relatedness, were reported in 40% of patients ($n = 18$). Anemia was most frequent (33%, $n = 15$), followed by neutropenia (11%, $n = 5$) and thrombocytopenia (2%, $n = 1$).

Twenty-six patients experienced Grade 3 AEs (regardless of relatedness), and no Grade 4 AEs were reported. Eleven Grade 3 AEs in 9 patients (20%) were considered related to BGB-290: anemia (11%, $n = 5$), neutropenia (7%, $n = 3$), hypophosphatemia (2%, $n = 1$), paresthesia (2%, $n = 1$), nausea (2%, $n = 1$), and fatigue (2%, $n = 1$).

Serious AEs (SAEs) were reported in 25 patients, and for 3 patients they were considered related to BGB-290: anemia ($n = 2$) and nausea ($n = 1$). Three patients discontinued study drug because of an AE: vomiting ($n = 1$), oral paresthesia ($n = 1$), and right neck cutaneous metastases ($n = 1$).

Four patients experienced a fatal AE ≤ 28 days after the last BGB-290 dose. All deaths were due to complications of the underlying malignancy, and none was considered related to BGB-290.

Four patients experienced AEs that were considered dose-limiting toxicities (DLTs): Grade 2 nausea that persisted despite optimal standard medical therapy in 2 patients; Grade 2 anorexia and Grade 2 nausea in 1 patient, and Grade 2 nausea and Grade 2 paresthesia in 1 patient. Based on the encountered DLTs and the overall safety profile of BGB-290, the MTD of BGB-290 was determined to be 80 mg PO BID (160 mg/day).

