9.1.5. Laboratory Test Abnormalities

Abnormal laboratory findings (eg, hematology or chemistry) or other abnormal assessments (eg, ECGs, x-rays, or vital signs) that are judged by the investigator as clinically significant will be

recorded as AEs or SAEs if they meet the definition of an AE (as defined in Section 9.1.1) or an SAE (as defined in Section 9.2). Clinically significant abnormal laboratory findings or other abnormal assessments that are detected during the study or are present at baseline and significantly worsen following the start of the study will be reported as AEs or SAEs. However, clinically significant abnormal laboratory findings or other abnormal assessments that are associated with the disease being studied, unless judged by the investigator as more severe than expected for the patient's condition, or that are present or detected at the start of the study and do not worsen, will not be reported as AEs or SAEs. They should be reported as AEs or SAEs if they induce clinical signs or symptoms, need active intervention, require a dose hold or permanent discontinuation, or are clinically significant in the opinion of the investigator.

The investigator will exercise his/her medical and scientific judgment in deciding whether an abnormal laboratory finding or other abnormal assessment is clinically significant.

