6.5.2 Adverse Events

AEs will be graded by the investigators using NCI CTCAE v4.03. The AE verbatim descriptions (investigator terms from the CRF) will be classified into standardized medical terminology using the Medical Dictionary for Regulatory Activities (MedDRA). Adverse events will be coded to the MedDRA (Version 22.0 or higher) lower level term closest to the verbatim term. The linked MedDRA preferred term (PT) and primary system organ class (SOC) are also captured in the database.

A treatment-emergent adverse event (TEAE) is defined as an AE that had an onset date on or after the date of the first dose of study treatment through 30 days after the last dose (permanent discontinuation of study treatment) or initiation of new anticancer therapy. Only those AEs that were treatment emergent will be included in summary tables. All AEs, treatment emergent or otherwise, will be presented in patient data listings.

An overview table of patients with at least one TEAE will be presented, as the number (percentage), with the incidence of following:

- patients with any TEAE
- patients with any TEAE with Grade 3 or higher
- patients with any serious TEAE
- patients with any TEAE leading to death
- patients with any TEAE leading to treatment discontinuation
- patients with any TEAE leading to dose modification
 - patients with any TEAE leading to dose interruption
 - patients with any TEAE leading to dose reduction
- patients with any treatment-related TEAE
- patients with any treatment-related TEAE with Grade 3 or higher
- patients with any treatment-related serious TEAE

- patients with any treatment-related TEAE leading to death
- patients with any treatment-related TEAE leading to treatment discontinuation
- patients with any treatment-related TEAE leading to dose modification
 - patients with any treatment-related TEAE leading to dose interruption
 - patients with any treatment-related TEAE leading to dose reduction

Summaries of all above TEAEs will also be reported as the number (percentage) of patients by SOC and PT.

Summaries of all TEAEs, SAE, Grade 3 or higher TEAEs, treatment-related TEAEs, and TEAE leading to treatment discontinuation will also be provided by PT only in descending order of frequency.

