All TEAEs, SAE, Grade 3 or higher TEAEs, treatment-related TEAEs and TEAEs leading to treatment discontinuation will also be summarized by SOC, PT, and maximum severity. A patient will be counted only once by the highest severity grade according to CTCAE v.4.03 within an SOC and PT, even if the patient experienced more than 1 TEAE within a specific SOC and PT.

Patient data listings of all AEs, SAEs, treatment-related AEs, Grade 3 or above AEs, AEs that led to death, AEs that led to treatment discontinuation, and AEs that led to dose modification will be provided.

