6.5.4 Laboratory Values

Laboratory safety tests of serum chemistry and hematology will be evaluated for selected parameters described in Table 3. The actual value and the change from baseline to each post-baseline visit and to the end of treatment will be summarized by visit using descriptive summary statistics (n, mean, standard deviation, median, minimum, maximum for continuous variables).

Urinalysis includes blood, protein, ketones, glucose, red blood cells, and white blood cells. Urinalysis results will not be summarized descriptively by visit.

Laboratory parameters that are graded in NCI CTCAE (v.4.03) will be summarized by shifts from baseline CTCAE grades to maximum post-baseline grades. In the summary of laboratory parameters by CTCAE grade, parameters with CTCAE grading in both high and low directions

will be summarized separately. Number (percentage) of patients with abnormal postbaseline laboratory values will be summarized.

Patient data listings of selected hematology and serum chemistry parameters, and urinalysis will be provided.

A summary of the liver function test abnormalities will also be presented based on Hy's law laboratory criteria defined as 1) Alanine aminotransferase (ALT) or Aspartate aminotransferase (AST) > 3 x ULN, 2) Total bilirubin (TBL) > 2 x ULN and 3) Alkaline phosphatase (ALP) < 2 x ULN and ALP ≥ 2 x ULN for patients with 1) and 2), at any postbaseline visit.

Table 3. Serum Chemistry, Hematology, and Urinalysis Laboratory Tests

Serum Chemistry	Hematology	Urinalysis
Alkaline phosphatase (ALP)	Hemoglobin	Blood
Alanine aminotransferase (ALT)	Platelet counts	Protein
Aspartate aminotransferase (AST)	White blood cell (WBC) count	Ketones
Albumin	Neutrophil	Glucose
Total bilirubin	Lymphocyte	Red blood cells
Blood Urea Nitrogen		White blood cells
Creatinine		
Chloride		
Phosphate		
Glucose		
Lactate dehydrogenase		
Total Protein		
Potassium		
Sodium		

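### SAP 6.5.2 has no rule that counts a patient once across related preferred terms, so a cytopenia can be split between diagnosis and laboratory rows and its adverse-event rate understated

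*SAP*

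**What the plan says.** SAP 6.5.2 sets the coding level ("Adverse events will be coded to the MedDRA (Version 22.0 or higher) lower level term closest to the verbatim term") and adds that "The linked MedDRA preferred term (PT) and primary system organ class (SOC) are also captured in the database". Tabulation follows from that. An overview table counts patients with any event in each category: Grade 3 or higher, serious, fatal, treatment-related, and leading to discontinuation, interruption or reduction. Below it, "Summaries of all above TEAEs will also be reported as the number (percentage) of patients by SOC and PT". The main categories "will also be provided by PT only in descending order of frequency", and are also shown by SOC, PT and maximum severity. The counting rule is that "A patient will be counted only once by the highest severity grade according to CTCAE v.4.03 within an SOC and PT".

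Neither SAP 6.5.2, the rest of the SAP nor protocol 10.6.2 defines a grouped term, a standardised query or an adverse-event-of-special-interest category.

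Two protocol sections govern what a site records. Section 9.4.1 asks for the diagnosis, when known, in place of its signs. Section 9.1.5 covers "Abnormal laboratory findings (eg, hematology or chemistry) or other abnormal assessments": those judged clinically significant are reported as adverse events, including when they require a dose hold or permanent discontinuation.

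SAP 6.5.4 adds laboratory tables that do not depend on adverse-event coding: "Laboratory parameters that are graded in NCI CTCAE (v.4.03) will be summarized by shifts from baseline CTCAE grades to maximum post-baseline grades", together with the number and percentage of patients with abnormal post-baseline values. Its Table 3 includes hemoglobin, platelets, white cells, neutrophils and lymphocytes.

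**The concern.** One low count can reach the database by two routes: as a diagnosis such as anemia, or as a laboratory finding such as a decreased hemoglobin. If the two wordings code to different PTs, no adverse-event table counts the patients who had that cytopenia by either route. An SOC total does not repair this if the two PTs also sit in different SOCs. A reader cannot add the rows, because a patient recorded under both would be counted twice.

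At stake is a stated secondary objective: the incidence, timing and severity of treatment-emergent events (SAP 3.2). Hematologic counts also carry weight in the protocol's own argument. Section 1.5 supports the chosen dose partly by fewer treatment-related events of anemia and neutropenia. In section 1.4.2.3, anemia (5 patients) and neutropenia (3) are the two largest entries among the related Grade 3 events. How often such events were related, serious or led to a dose change is what the split would blur. With about 110 planned centers, wording may also vary from site to site.

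**Working it through.** **Step 1: does any planned table pool the routes?**
- Overview table (SAP 6.5.2): unaffected by a PT split, but it does not isolate cytopenias.
- SOC and PT, PT only, and SOC/PT/maximum severity tables (SAP 6.5.2): patients are counted once within a PT, with no rule across PTs.
- Laboratory shift and abnormal-value tables (SAP 6.5.4): these capture the cytopenia and its grade by either route, but not relatedness, seriousness or dose action. Protocol 7.5 also lets local results guide dose changes while central results are the official record where available. A hold triggered by a local value may therefore not appear in the shift table at that grade.
- Dose-modification reasons (SAP 6.5.1): summarised, but the documents do not say that the reasons name the toxicity.

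No table gives a pooled count of cytopenia patients by relatedness, seriousness or dose action.

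**Step 2: reproduce the Phase 1 rates (protocol 1.4.2.3, 45 patients, regardless of relatedness).** Anemia 15/45 = 33.3%; neutropenia 5/45 = 11.1%; thrombocytopenia 1/45 = 2.2%. These match the stated 33%, 11% and 2%. The rows sum to 15 + 5 + 1 = 21, while the same section reports 18 patients with any hematologic event (18/45 = 40%). Hematologic rows overlap within patients, so rows cannot simply be added.

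**Step 3: illustrate the possible loss.** Let p be the combined rate and s the share of affected patients coded only to the laboratory PT. The diagnosis row then shows p × (1 − s).

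Assumptions: p equals the Phase 1 rate; s runs from 0% to 50%; the diagnosis and laboratory-decrease wordings have separate PTs. The documents give no value for s, do not list the PTs, and do not say whether the Phase 1 rates were already pooled. Patient counts use the planned 64 per arm.

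| Concept | s = 0% | s = 10% | s = 25% | s = 50% |
|---|---|---|---|---|
| Anemia, p = 33.3% | 33.3% (21.3 of 64) | 30.0% (19.2) | 25.0% (16.0) | 16.7% (10.7) |
| Neutropenia, p = 11.1% | 11.1% (7.1) | 10.0% (6.4) | 8.3% (5.3) | 5.6% (3.6) |
| Thrombocytopenia, p = 2.2% | 2.2% (1.4) | 2.0% (1.3) | 1.7% (1.1) | 1.1% (0.7) |

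The relative loss equals s. At s = 0 nothing is lost.

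**Step 4: why adding rows does not help.** If a further share b of affected patients is recorded under both terms, the laboratory row shows p × (s + b), and the two rows sum to p × (1 + b). For anemia with s = 25% and b = 10% (both assumed), the rows are 25.0% and 33.3% × 0.35 = 11.7%. Their sum is 36.7%, against a true 33.3%. From the tables alone, the reader knows only that the rate lies between 25.0% and 36.7%.

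**The case against.** The strongest case against is that nothing shows that a split will occur. The diagnosis-first rule in protocol 9.4.1 is aimed at this duplication, and its example is to record hepatitis rather than raised transaminases or bilirubin. The dose-modification table in protocol 6.1.4 also gives sites the diagnosis names anemia, neutropenia and thrombocytopenia. This largely stands: the rule reduces splitting. It does not exclude it, because section 9.1.5 keeps the laboratory route open and no instruction says how a low count is to be worded.

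Second, the cytopenias are measured directly in SAP 6.5.4, and patient listings of serious, related, Grade 3 or above, and dose-modifying events are planned. This stands for incidence by grade, so it would be wrong to say that no table counts cytopenias. It does not supply pooled counts by relatedness, seriousness or dose action. A grouping assembled from listings after unblinding would be post hoc.

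Third, a reader might infer that cytopenias are the drug's main toxicities and cause most dose changes. The documents do not support that. In protocol 1.4.2.3 the most frequent related events are nausea (51%) and fatigue (29%), and thrombocytopenia occurred in 1 of 45 patients. All four patients with dose-limiting toxicities had nausea, and none of the three discontinuations for an adverse event was for a cytopenia. Section 1.5 names anemia and nausea together for dose interruptions. The sentence "Hematologic AEs are of interest in this study" describes the Phase 1 study, not this trial. Anemia and neutropenia carry the case, supported by bone marrow inhibition as a main nonclinical finding (protocol 1.4.1.1).

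Fourth, sites are blinded and randomization is stratified by region, so recording habits should be similar in the two arms. This stands: a split could lower rows in both arms, but nothing points to bias between them.

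**Conclusion.** The gap is real and small. SAP 6.5.2 has no rule that counts a patient once across related PTs, and the protocol leaves two recording routes open. A cytopenia can therefore be split, and its diagnosis row can then understate related, serious and dose-modifying events. The coding sentence itself is routine; what is missing is a grouping rule.

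A reader might go further and conclude that the rates will be understated. The documents do not support that, because they contain no coding split. The 33% to 17% range for anemia rests on an assumed s of 0% to 50%, a Phase 1 rate taken as the combined rate, and separate PTs for the two wordings. Nor do the documents show that the same proportional loss would apply to the related, serious and dose-modifying subsets.

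Only descriptive safety tables are affected. The PFS test, its significance level and its power are not.

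**What to change.** Before unblinding, add to SAP 6.5.2 a fixed list of grouped terms: anemia, neutropenia, thrombocytopenia and leukopenia. Each group combines the diagnosis PT with the corresponding laboratory-decrease PT, and the PTs are listed by name against the MedDRA version in use. Count each patient once per group, at the highest grade, for:
- any treatment-emergent event;
- Grade 3 or higher;
- serious;
- treatment-related;
- leading to interruption, reduction or discontinuation.

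Keep the single-PT tables as planned, so that the grouping can be checked against its components.

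The cost is one term list and a few extra tables from data already collected. The stated cytopenia rates may come out less favourable than the single-PT rows.

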9.4.3. Persistent or Recurring Adverse Events

A persistent AE is one that extends continuously, without resolution, between patient evaluation time points. Such AEs should only be recorded once on the AE eCRF (and SAE report, if applicable). If a persistent AE worsens in grade, the worst grade should be recorded for the entire event.

A recurrent AE is one that occurs and resolves between patient evaluation time points, and subsequently recurs. All recurrent AEs should be recorded separately on the eCRF (and SAE report, if applicable).

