10.6.2. Adverse Events

The AE will be coded using MedDRA Version 22.0 or higher and graded using the current version of NCI-CTCAE.

A TEAE is defined as an AE that had an onset date on or after first study treatment or was worsening in severity from baseline (pretreatment) up to 30 days following permanent study drug discontinuation or initiation of new anticancer therapy, whichever occurs first. All TEAEs will be included in summary tables and in-patient data listings.

The incidence of TEAEs will be reported as the number (percentage) of patients with TEAEs by system organ class (SOC) and preferred term (PT). A patient will be counted only once by the highest grade according to NCI-CTCAE Version 4.03 within an SOC and PT, even if the patient experienced more than one TEAE within a specific SOC and PT. The number (percentage) of patients with TEAEs will also be summarized by relationship to the study treatment.

Treatment-related AEs include those events considered by the investigator to be related to study treatment or with missing assessment of the causal relationship. Serious AEs, deaths, TEAE of Grade ≥ 3 , study drug-related TEAEs, and TEAEs that led to study drug withholding or permanent discontinuation will also be summarized.

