8 CHANGES IN THE PLANNED ANALYSIS

- The Per-Protocol (PP) analysis set defined in the protocol BGB-290-303 (version 1.0, 2020-02-13) will not be considered in the analysis.
- Progression-free survival 2 (PFS2) by investigator assessment as secondary efficacy endpoints defined in the protocol BGB-290-303 (version 1.0, 2020-02-13) will not be considered in the analysis.
- Confirmation of response will not be required for ORR in randomized clinical studies per RECIST v1.1. No confirmation of response required for the analysis of DOR and Time to response to be consistent with analysis of ORR.
- The stratification factor of HRD status (LOH_{high} versus LOH_{low} versus unknown) will not be included as strata for PFS, OS, and TSST nor covariate in primary or secondary analyses due to high rate of patients with unknown LOH reported. And the Region will have three strata (China/Hong Kong/Taiwan versus Australia/Europe/North America versus Japan/South Korea/rest of world [ROW]) for PFS, OS, TSST, and covariate in primary or secondary analyses after combining patients in Japan/South Korea with patients in ROW as small number of patients were enrolled in Japan and no patients were enrolled in South Korea.
- No PK parameters will be derived and reported in clinical study report. The definition of PK analysis set is thus modified as all patients who have at least one plasma concentration.

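### SAP 6.5.2 drops the protocol's worsening-from-baseline route from the TEAE definition without declaring it, so an AE record opened before dosing that worsens on treatment would miss the TEAE tables

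*SAP*

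**What the plan says.** Protocol 10.6.2 defines a TEAE by onset on or after first study treatment, and then adds a second route: "or was worsening in severity from baseline (pretreatment) up to 30 days following permanent study drug discontinuation", with the window closing at that point or at new anticancer therapy, whichever is earlier.

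SAP 6.5.2 defines it by onset alone: an event counts if it "had an onset date on or after the date of the first dose of study treatment". Its window runs until 30 days past the final dose or the start of new anticancer therapy. It then sets what is tabulated, "Only those AEs that were treatment emergent will be included in summary tables", and what is listed, "All AEs, treatment emergent or otherwise, will be presented in patient data listings".

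Protocol 9.4.3 governs an event that continues without resolving. It is entered once, and "If a persistent AE worsens in grade, the worst grade should be recorded for the entire event".

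SAP Section 8, headed "CHANGES IN THE PLANNED ANALYSIS", has five items. None concerns the TEAE definition.

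**The concern.** The frequency, timing and severity of TEAEs form a secondary objective (Protocol 2.2) and a secondary endpoint (SAP 4.2). The SAP narrows the definition of that endpoint, and the section meant to record departures from the protocol does not mention it.

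The narrowing would do no harm if every on-treatment worsening were entered as a new AE with its own post-dose onset date. Protocol 9.4.3 prevents that for one group of events. An event recorded before dosing that persists stays on its single record, so its onset date remains before first dose even if it reaches a higher grade or becomes fatal on study drug. By the protocol's definition it is treatment-emergent; by the SAP's it is not. The events concerned are mainly serious ones, in a placebo-controlled comparison where the TEAE tables are the main AE summary.

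**Working it through.** The plan gives no figure to reproduce here. The check is a side-by-side reading.

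1. **Routes to a TEAE.** Protocol 10.6.2 has two: onset, or worsening from pretreatment. SAP 6.5.2 has one: onset. No other SAP section restores the second.

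2. **End of the window.** Protocol 10.6.2 takes the earlier of 30 days after discontinuation and new anticancer therapy. SAP 6.5.2 names both limits but does not say how they combine.

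3. **Declaration.** The five items in SAP Section 8 are the per-protocol set, PFS2, confirmation of response, the strata, and the PK parameters and set. The TEAE definition is not among them.

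4. **Which AE records can carry a pre-dose onset.** Protocol 9.3.1 limits reporting between consent and first dose to SAEs. Screening falls within 28 days before randomization (Protocol 5.1) and treatment starts within 4 days after it (Protocol 5.3), so this interval is at most about 28 + 4 = 32 days.

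5. **What happens when something already present worsens on treatment.**
   - Relevant conditions present before consent go to medical history, with baseline severity if ongoing (Protocol 7.2.2). Their worsening is itself an AE (9.1.1), and baseline abnormalities that significantly worsen are reported as AEs or SAEs (9.1.5). Entered as new records after first dose, these meet the SAP definition.
   - A nonserious AE that becomes serious gets a second record with a new onset date (9.4.2). This does not help an event recorded before dosing, which is already an SAE.
   - A persistent AE that rises in grade stays on one record (9.4.3). This is the case that escapes.

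6. **Both definitions applied to that case.** Take, as an illustration, an SAE that starts after consent, is Grade 3 and ongoing at first dose, and reaches Grade 4 two weeks later. Under the protocol it qualifies by worsening. Under the SAP its onset is too early, so it does not. It is then absent from the counts of any, serious, and Grade 3 or higher TEAEs, and, if it becomes fatal, of TEAEs leading to death. Some tables in SAP 6.5.2 are labelled as SAE tables rather than serious TEAE tables, but the restriction to treatment-emergent events is stated for the summary tables generally.

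7. **Where it would still be seen.** The summary of all deaths (SAP 6.5.3), laboratory shifts from baseline grade to worst post-baseline grade (6.5.4), vital sign changes (6.5.5) and ECG summaries (6.5.6) do not use the TEAE flag. The AE listings include events that are not treatment-emergent, with separate listings for serious, Grade 3 or above and fatal events.

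**The case against.** The strongest reply is that the recording rules already close most of the gap. Pre-existing conditions are history, and their worsening becomes a new AE. What is left is an SAE opened before dosing, unresolved at first dose, in a patient who is nonetheless randomized and treated, and which then worsens. The exclusions in Protocol 4.2 (most unresolved Grade 2 or higher acute effects of prior therapy, active infection needing systemic treatment, active bleeding, significant intercurrent illness) make that uncommon. This stands, and it sets the size of the point.

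A reader might infer that such events vanish from every safety table. The documents do not support that: step 7 of the working lists the outputs that do not depend on the TEAE flag. A death, for example, is still tabulated; only the count of TEAEs leading to death could miss it.

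A reader might also infer that common residual effects of chemotherapy, such as anemia or neuropathy, would be lost when they worsen. That does not follow either, since Protocol 9.1.1 and 9.1.5 make the worsening reportable in its own right. One uncertainty remains: 9.1.1 does not say which onset date to enter. If sites used the original date the loss would be wider, but nothing in the documents instructs them to.

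A further objection is that restoring the clause may not be enough. A single record carrying only the worst grade may not show whether the worsening came before or after first dose. This is a fair criticism of a one-clause remedy, and the fix needs a handling rule. It does not remove the conflict between the two definitions.

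On the window, it can be said that AE collection itself stops at the earlier date (Protocol 9.3.1). That is largely right. Related SAEs are still reported afterwards, however, so the SAP should say how its two limits combine.

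**Conclusion.** The point holds in a limited form. The SAP's TEAE definition is narrower than the protocol's, and the change is undeclared. Read literally, it keeps an AE record with pre-dose onset that worsens on treatment out of the TEAE-based tables, and out of those only.

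The number of affected events cannot be estimated from the documents. It is probably small and could be zero. A reader might try to put a count on it by assuming that 1% to 4% of the 128 patients have an SAE before dosing: 0.01 × 128 = 1.28 and 0.04 × 128 = 5.12, or about 1 to 5 patients. The documents give no such rate, and the calculation counts any pre-dose SAE rather than those that persist and then worsen. It should not be read as the number of events at stake.

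The conclusion assumes that sites follow Protocol 9.3.1 and 9.4.3 as written, and that a record kept as one event keeps its original onset date. The consequence is minor, but it touches a named secondary endpoint and mainly serious events.

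**What to change.** Restore the protocol's definition in SAP 6.5.2: onset on or after first dose, or worsening in severity from the pretreatment level, up to 30 days after the last dose or the start of new anticancer therapy, whichever is earlier. This also settles the end of the window.

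Add a handling rule. A record opened before dosing and ongoing at first dose counts as treatment-emergent if its grade rose, or its outcome became fatal, after first dose. If the timing of the worsening cannot be determined, it counts by default. SAP Appendix 10.1 already resolves doubt in that direction; it does so for partial dates, so the extension should be written out.

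If the sponsor prefers onset only, Section 8 should declare and justify the change, and the plan should state that on-treatment worsening is entered as a new AE with its own onset date. That would also have to be reconciled with Protocol 9.4.3.

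The cost is one clause, one handling rule and the matching derivation, with a check of the few records open at first dose. The downside is that a few events already at their worst grade before dosing may be counted.
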